Sessions will be facilitated by registered counsellors (the equivalent of psychological technicians with four years of university training) and registered psychologists. A facilitators' handbook, with detailed descriptions of the content of each session and facilitation guidelines will be provided and facilitators will be trained on group therapy facilitation. Online sessions will be recorded so that they could be reviewed during supervision.

Control groups:

The control groups will be directed to make use of one of three digital applications (apps); i.e., Mood Flow, SilverCloud (guided), and SilverCloud (unguided).

Assessment schedule:

As part of the study, the experimental group intervention participants will complete a baseline assessment at the start of the study and process assessments every two weeks. Follow-up assessment will also be administered to monitor symptom change (i.e., 3-month post-treatment, 6-month post-treatment, and 1-year post-treatment). The control group will only complete the baseline assessment and a 3-month follow up assessment.

Management of risk

If during the initial screening and recruitment or follow-up assessments, any participant endorses a "2" (more than half the days) or "3" (nearly every day) on the PHQ-9 (Thoughts that you would be better off dead or of hurting yourself in some way), they will receive an automated message that provides a list of emergency resources. The email and text message will be sent immediately after endorsing the item. Students who report active suicidality with intent at any time during the study will be referred to appropriate campus-based crises services, and national suicide helplines.

Statistical Analyses:

Data will be cleaned and analysed with SPSS (version 27). Descriptive statistics will be used to summarise participant characteristics, attendance rates, and primary outcomes.

We will evaluate aggregate intervention effects, as well as evaluate aggregate

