All collected electronic data will be password protected and will be accessed only by authorized personnel. The data will only be used for this study and will be destroyed after a three-year period. Scientific publications or presentations on the results will only report analyses on an aggregated level.

(b) *Discomfort*. If participants experience discomfort when completing the study questionnaires or throughout the intervention, they can refuse to answer any questions. Further, all participants may choose to discontinue the assessment/intervention and/or withdraw from the study. This is outlined in the relevant Informed Consent Form.

Clinical Risk and Benefits. There are risks with any intervention, most specifically that they will not work or that a person might get frustrated by this intervention approach. However, there also are benefits as the group nature of this intervention shows students that they are not alone. There is no reason to believe this intervention would not prove effective in university students given past research showing that psychological group interventions in depressed and anxious higher education students are effective (Conley et al., 2015). Additionally, there are a number of benefits for the greater community. Namely, the study will advance our collective understanding of the feasibility in using psychological skills training group interventions for treating symptoms of depression and anxiety in university students. This information may then be utilized to develop more effective intervention programs.

Institutional permission:

We will seek institutional permission from the appropriate authorities at Stellenbosch University to conduct this study.

MONITORING, ASSESSMENT, AND RISK MANAGEMENT OF PARTICIPANTS

(a) The PIs will have the responsibility for continuous monitoring of data and safety of subjects in the study. Data and safety monitoring will take place continuously throughout the study's duration.

(b) Following the initial baseline assessment, those participants who report severe symptoms of depression, or suicidality will receive an automated message that provides a list of emergency resources.

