- (c) Students' identified as being at risk will be immediately referred to the SSVO for further assessment and management. They will not be discharged from the RCT, but we will insist that they are also receiving individual care at the same time and that they are aware of the crises services available to students' (i.e. ER 24 crises line). The group facilitators will manage this referral process in collaboration with the SSVO.
- (d) All administrators will be trained and supervised by [name].
- (e) Of note, the administrators will not specifically probe or assess suicide risk. However, in the unlikely situation that a participant explicitly states that he/she is suicidal, the participant would be provided with a list of emergency resources, per email and phone text message.
- (f) We will report both adverse events and all serious adverse events that occur during the course of the study to the Institutional Review Board (IRB). Specifically, we will record all adverse events in a tracking log based on IRB templates, which will be submitted to the IRB at each continuing review.
- (g) At the time of the continuing review we will provide the IRB with a summary of any unexpected and related adverse events as well as any other unanticipated problems that occurred since the last continuing review.
- (h) Adverse events and unanticipated problems will be reported to the IRB per PHRC reporting guidelines. We will report to the IRB any unanticipated problems and adverse events that occur: (a) during the conduct of the study, (b) after study completion, or (c) after subject withdrawal or completion. Reports will be submitted within 5 working days/7 calendar days of the date the investigator first becomes aware of the problem.
- (i) Throughout the study there may be circumstances where a subject's participation may be terminated by the PI without the subject's consent. Specifically, potential reasons for participation termination may include: (a) increased participant suicidality, and (b) participant no longer satisfies inclusion criteria.

DATA STORAGE

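### The suicide-risk passages differ on what triggers the automated message, do not link their responses or agree on staying in the trial, and give SSVO referral to a role described only for GCBT

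*Combined protocol and SAP*

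**What the plan says.** Two parts of the protocol deal with suicide risk.

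**METHODS, Management of risk.** At initial screening and recruitment, or at a follow-up assessment, a score of 2 or 3 on the self-harm item sets off a message. The text identifies the item as "nearly every day) on the PHQ-9 (Thoughts that you would be better off dead or of hurting yourself in some way", and the response is "they will receive an automated message that provides a list of emergency resources". The same paragraph adds a second rule: "Students who report active suicidality with intent at any time during the study will be referred to appropriate campus-based crises services", together with national helplines. No role is named for that referral.

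**MONITORING, ASSESSMENT, AND RISK MANAGEMENT OF PARTICIPANTS.**
- Item (b), following the baseline assessment: "those participants who report severe symptoms of depression, or suicidality will receive an automated message that provides a list of emergency resources".
- Item (c): students "identified as being at risk will be immediately referred to the SSVO for further assessment and management". They stay in the trial and must also be in individual care. "The group facilitators will manage this referral process in collaboration with the SSVO".
- Item (e): if someone states outright that he or she is suicidal, "the participant would be provided with a list of emergency resources, per email and phone text message".
- Item (i): the principal investigator may end a student's participation without consent, and increased suicidality is one of the possible reasons.

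Facilitators are described under the details of the GCBT intervention, as the counsellors and psychologists who lead its sessions. The Control groups paragraph directs the other three arms to apps and describes no facilitator.

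**The concern.** Whoever programs the questionnaire, and whoever handles an alert, needs one rule. Here the trigger, the timing, the response, the student's trial status and the responsible role are spread over five places that do not refer to one another. Staff who follow one place may leave out a student whom another place covers. What is at stake is the safety of participants in a trial that targets symptoms of depression and anxiety. It is also whether the risk procedure is carried out in the same way at each assessment and in each arm.

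**Working it through.** The documents give no figure on this point, so the check is a comparison of the text.

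| Place | Trigger | When | Response | Who acts |
|---|---|---|---|---|
| Management of risk, first rule | PHQ-9 self-harm item scored 2 or 3 | Screening/recruitment or follow-up | Automated resource list | Automated |
| Management of risk, second rule | Active suicidality with intent | Any time | Referral to campus crisis services and national helplines | Not stated |
| Monitoring (b) | Severe depressive symptoms, or suicidality; no threshold | Following baseline | Automated resource list | Automated |
| Monitoring (c) | At risk; not defined | Not stated | Immediate SSVO referral, concurrent individual care, stays in trial | Group facilitators with the SSVO |
| Monitoring (e) | Explicit statement of being suicidal | Not stated | Resource list by email and text | Not stated |
| Monitoring (i) | Increased suicidality | Throughout the study | Possible termination without consent | Principal investigator |

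Running cases through the table:

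1. *Severe depressive symptoms at baseline, self-harm item scored 0 or 1.* Item (b) sends the message. The item rule in Management of risk does not. For a score of 1 it is also unclear whether (b) counts the answer as suicidality.
2. *Self-harm item scored 2 for the first time at 3 months.* Management of risk sends the message. Item (b) names only the period following baseline, so follow-up is named in one place and not in the other.
3. *A student says that he or she is suicidal, and no intent is reported.* Item (e) gives a resource list. Item (c) gives immediate SSVO referral if the student counts as at risk, which is undefined. The crisis-service referral does not apply without intent. The plan does not say whether (e) comes before (c), is added to it, or stands in its place.
4. *A student already referred as at risk becomes more suicidal.* Item (c) says the student is not discharged. Item (i) says that participation may be ended. Nothing tells the two situations apart.
5. *An at-risk student in Mood Flow, SilverCloud guided or SilverCloud unguided.* Item (c) requires the SSVO referral and gives it to group facilitators. No such role is described for these three of the four arms.

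Cases 1 and 2 decide how the message is programmed. In case 1 the two rules give different results for the same answers. Cases 3 to 5 need a link, a distinction or a named role that the text does not supply.

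**The case against.** The best defence is that the passages are cumulative: the message first, then referral where risk is identified. Item (c) itself combines several steps, and item (e) is about what administrators do. Much of this stands, and it rules out several stronger readings that a reader might infer.

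- *Items (c) and (e) contradict each other.* This requires reading (e) as giving a resource list and nothing more. It does not say that, and a student can receive the list and also be referred. What remains is that the plan states no sequence.
- *Item (b) applies at baseline alone.* The text does not exclude later assessments, and Management of risk expressly covers follow-up. The difference lies in what each place names.
- *App-arm students have no facilitator and no route to referral.* No passage says that they lack one. The Privacy paragraph under Potential risks speaks generally of respective group facilitators, although about an attendance register, and the support in SilverCloud guided is not described. The referral for suicidality with intent applies in every arm, and the principal investigators are responsible for the safety of all participants. The supported statement is narrower: the role that (c) names is described only for GCBT.
- *Three quarters of the sample is affected.* Three arms of at least 100 out of at least 400 is 3 × 100 / 400 = 75%. That is the share in arms with no described facilitator, not the share who would need referral.
- *Individual care becomes an uneven co-intervention that biases the comparison.* Item (c) requires referral and individual care without limiting them by arm, so imbalance is not established.

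The defence does not remove the two triggers for one message, the undefined terms, the tension between (c) and (i), or the missing description of who runs SSVO referrals for the app arms.

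**Conclusion.** The point holds as a consistency problem in the risk procedure, and the passages must be reconciled. It goes beyond missing detail, because one automated message has two triggers that treat the same student differently, and because the SSVO referral process has no described operator in three of four arms. The conclusion rests on the wording alone and on one reading: that the sections are meant to describe a single procedure, since nothing in them says otherwise.

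Its size in students cannot be given, because the documents state no at-risk rate. For the same reason no effect on the between-arm comparison is claimed. Nothing here says which trigger, response or rule on staying in the trial is right. It should be changed, for participant safety.

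**What to change.** Reconcile Management of risk with items (b), (c), (e) and (i) in one trigger-and-response table, and have the other places refer to it. The table should:
- apply at every assessment and in all four arms;
- define the terms now left open (at risk, suicidality, severe symptoms) and relate them to the PHQ-9 item;
- say whether the responses are cumulative and in what order;
- settle how (c) and (i) fit together.

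Then set the automated message to match the table, and state which existing role runs SSVO referrals for students in the app arms. The clinical leads decide the thresholds and actions; none is proposed here.

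The cost is protocol wording and a check of the message settings. Sample size and analysis do not change.

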differences across arms using conventional intent to treat (Gupta, 2011) and complier average causal effect (CACE) (Angrist, Imbens, & Rubin, 1996) analyses based on inverse probability weights to deal with loss to follow-up (Robins, Rotnitzky, & Zhao, 1994). Log-binomial regression will be used to estimate remission and to report adjusted prevalence ratios with 95% CIs. If convergence problems occur, we will fall back on Poisson regression with robust variance estimation. We will calculate numbers needed to treat for each outcome (remission of anxiety, depression, and combined PHQ-ADS). To estimate CACE, we will use two-stage least squares (Wooldridge, 2020) and control function procedures (Clarke & Windmeijer, 2012). We will evaluate the validity of the assumptions needed for this estimation and conduct sensitivity analyses. Distributions and correlates of dropout and missing data will be provided in reports.

Process analyses will allow us to investigate the pathways through which the intervention affects the outcomes by investigating intermediate effects of the individual intervention rule (IIR) in predicting responses in the five-minute process assessments that will be carried out every two weeks with students in the intervention arm over the 10 weeks of the intervention. The instrument used in these process assessments, the CBRSS (Miner, Schueller, Lattie, & Mohr, 2015), measures frequency of applying core cognitive skills (CSF) and core behavioral skills (BSF) during times of stress. We will also use the 4-item screening version of the GAD-7 and PHQ-9, the PHQ-4 (Kroenke, Spitzer, Williams, & Löwe, 2009), to assess anxiety-depression over each 2-week period. We will begin by investigating associations of the CSF and BSF measures both cross-sectionally and with a 2-week time-lag in predicting PHQ-9 scores. Our interest will be in determining whether CSF and BSF predictor PHQ-9 scores and if these associations increase over time.

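### Item (c) keeps at-risk students in the trial, item (i) lets the PI end participation for increased suicidality; the two are not reconciled, and termination is not limited to the intervention

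*Combined protocol and SAP*

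**What the plan says.** All references are to the combined protocol and SAP.

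- **Monitoring section, item (c).** Students identified as at risk are referred at once to the SSVO. The text continues: "They will not be discharged from the RCT, but we will insist that they are also receiving individual care at the same time". On who handles this: "The group facilitators will manage this referral process in collaboration with the SSVO".
- **Monitoring section, item (i).** There may be circumstances in which "a subject's participation may be terminated by the PI without the subject's consent". The item adds that "potential reasons for participation termination may include: (a) increased participant suicidality, and (b) participant no longer satisfies inclusion criteria".
- **Inclusion Criteria (b).** The student must be enrolled at the university.
- **Management of risk.** A response of 2 or 3 on the PHQ-9 self-harm item, at screening or follow-up, triggers an automated list of emergency resources for any participant. Students who report active suicidality with intent are referred to campus crisis services and national helplines. Neither provision is limited by arm.
- **Statistical Analyses.** The plan evaluates "differences across arms using conventional intent to treat", and also complier average causal effects, with inverse probability weights for loss to follow-up. Remission of depression is one of the outcomes. Academic attrition is among the follow-up outcomes in the process analyses. Reports will describe dropout and missing data.

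**The concern.** There are two separate problems and one smaller gap.

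First, a student whose suicidality increases would ordinarily also be at risk, so both items can apply to the same person. One says the student stays in the trial; the other allows the PI to end participation. In a depression trial, staff should not have to work out the relation between two safety rules when a case arises.

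Second, item (i) does not say what happens to the outcome surveys. If ending participation also ends them, students drop out of the data after randomisation because of suicidality or because they left the university. Both reasons are related to what the trial measures, and an intent-to-treat comparison is meant to guard against such losses.

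The smaller gap is that item (c) gives the SSVO referral to group facilitators. The three control arms use apps, and the text does not say who manages that referral for their students.

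**Working it through.** No figure in the plan depends on this point, so the check is a comparison of texts.

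**Step 1: items (c) and (i).**

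| | Item (c) | Item (i) |
|---|---|---|
| Trigger | identified as at risk | increased suicidality; inclusion criteria no longer met |
| Force | categorical | permissive |
| Who acts | facilitators with the SSVO | PI |
| Result | stays in the RCT, with individual care | participation may be ended without consent |

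Neither trigger is defined in the monitoring section. The Management of risk section does give a threshold (PHQ-9 self-harm item scored 2 or 3), but only for the automated message, and does not link it to either item. Nothing says which item prevails. The overlap concerns suicidality only; the lost-eligibility reason does not touch item (c).

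**Step 2: what termination covers.** Item (i) speaks of participation. Under Potential risks, the paragraph on discomfort distinguishes leaving the assessment or intervention from withdrawing from the study, but only for the participant's own choice. No corresponding distinction is made for termination by the PI, and the reviewed text does not say whether surveys then continue or stop.

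**Step 3: link to the outcomes.** Increased suicidality is related to remission of depression. Loss of enrolment is related to academic attrition. Both reasons can therefore make missingness informative.

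**Step 4: can the planned weights repair it?** Let R = 1 if the outcome Y is observed, A the arm and X the measured variables. Each observed outcome is weighted by 1 / P(R = 1 | A, X). This recovers the result for all randomised students only if P(R = 1 | A, X, Y) = P(R = 1 | A, X), that is, if measured variables explain who is terminated. Item (i) turns on a change during the study and on a discretionary decision by the PI. The plan lists no variables for the weights and does not mention PI terminations, so the condition cannot be confirmed from the text.

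**Step 5: size.** The documents give neither a termination rate nor a remission rate. Neither the size nor the direction of any bias can be calculated.

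**The case against.** The strongest reply is that items (c) and (i) are compatible. Item (c) sets the default (refer, do not discharge), and item (i) is a discretionary reserve for worsening, held by a different person. That is a fair reading. A reader might infer that staff cannot comply with both items, and the documents do not support this: a PI who never uses the power in item (i) complies with both. What stands is that the text does not state this reading and gives no threshold for moving from one item to the other.

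A second reply is that the loss of outcome data is argued from silence, and that the consent form, which was not available for this review, may cover it. This is correct as far as it goes. The wording leaves the loss open; it does not prescribe it. The plan also already has intent-to-treat analysis, weights and dropout reporting. None of these says whether a terminated student is still surveyed.

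Three further inferences are tempting and should not be drawn:

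- **That the GCBT arm has two-weekly data on suicidality and the app arms have none.** The process assessments are confined to the intervention arm, but they are described as a skills measure (the CBRSS) and the PHQ-4. The documents do not show that they measure suicidality.
- **That termination before 3 months removes an app-arm student's only follow-up.** The Assessment schedule says: "The control group will only complete the baseline assessment and a 3-month follow up assessment". The Methods section, however, lists 3-, 6- and 12-month follow-up without limiting it by arm.
- **That app-arm students have no safety cover.** The automated message and crisis referral apply to all arms. Only the handling of the SSVO referral is unassigned.

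**Conclusion.** The point holds in two parts. Items (c) and (i) are unreconciled on suicidality: a default-and-exception reading is possible but unstated. Independently, item (i) is wide enough to end outcome collection for reasons related to the outcomes, which would work against the intent-to-treat plan and which the weights would correct only under a condition the plan does not address. The referral gap in the app arms is a smaller matter.

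The second part assumes that ending participation may include ending the surveys, which the reviewed text neither states nor excludes. No claim is made about how many students would be affected or which arm would be favoured. The change should be made mainly because the safety text is ambiguous, and because keeping follow-up open is cheap protection against informative loss.

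**What to change.** 1. **Reconcile the safety text.** The investigators must reconcile items (c) and (i) and state who manages the SSVO referral for students in the app arms. No view is taken here on which clinical rule should apply.
2. **Separate intervention from follow-up in item (i).** State that neither PI termination nor loss of student status by itself ends the scheduled outcome surveys, and that the student is analysed as randomised unless he or she withdraws consent. Any safety limit on contact is for the investigators to set when they reconcile the items.
3. **Report terminations.** Within the dropout reporting already planned, give PI terminations by arm and reason.

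The cost is protocol wording, consent wording if the form does not already cover this, and a few extra survey contacts with students who stopped the intervention or left the university.
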